### Interventions

LE options are main dishes ≤600 kcal because meals ≤600 kcal comply with the dietary recommendation for US adults (i.e., on average 2,000 kcal per day) assuming an energy repartition pattern of three main meal occasions, each accounting for 20–35 % of daily energy intake, and 1–2 snacking occasions, each accounting for 5–10 % of daily energy intake [27].

In the baseline availability conditions (C and CL) 1/10 main dishes on the menus will be 600 kcal or less and 9/10 will exceed 600 kcal. In the increased availability of lower energy options conditions (A and AL), the proportion of main dishes ≤ 600 kcal will be increased to 5/10 by replacing four of the > 600 kcal main dishes from the baseline availability conditions with lower energy main dishes, whilst holding the price of replaced menu items the same. The menu items with the highest and the lowest energy content will remain the same in order to ensure the range of energy is consistent across conditions. The difference in the mean energy content of the menus items between C/CL and A/AL conditions will be approx. the same for familiar and unfamiliar menus.

In the energy labelling conditions (L and AL) energy in kcal will be added next to each menu option and reference information on energy requirements will be displayed. The energy labelling format will be in line with the mandatory menu labelling policy published by the US Food and Drug Administration [28], which requires restaurants to:

- Disclose calories for standard menu items listed on menus and menu boards:
  - Calorie labelling is placed on the menu adjacent to the name or the price of the menu item in a manner in close proximity and clearly associated with the menu item;
- Include on menus a succinct statement concerning suggested caloric intake and a statement that additional nutrition information is available upon request:
  - The succinct statement ‘2,000 calories a day is used for general nutrition advice, but calorie needs vary’ must appear on the bottom of menu boards and at the bottom of each page of multi-page menus;

- The statement of availability 'Additional nutrition information available upon request' must appear on the bottom of the first page of a menu that lists standard menu items and at the bottom of the menu board
- They may be on the individual sign adjacent to the food itself, or on a separate, larger sign in close proximity to the food. The customer must be able to easily read the sign when making a selection.

In the no energy labelling conditions (C and A) there will be no kcal information next to menu options.

### 5.2. Measures of socioeconomic status

The socioeconomic status is a multi-faceted concept. Four measures of socioeconomic status will be included. Participants will be asked to report:

- their highest educational qualification;
- their number of years in higher education;
- their current employment status and main job title;
- their household income and their household composition;
- a subjective measure of their socioeconomic status using the MacArthur Scale of Subjective Social Status (SSS) [29].

### 5.3. Measure of health motivation

The **Food Choice Questionnaire**, developed by Steptoe et al. 1995 [30], measures the motives related to food choice, including health. We will use a short version of this questionnaire, the **single-item Food Choice Questionnaire** recently developed by Onwezen et al. 2019 [31].

## 6. STUDY FLOW

RECRUITMENT (Prolific)	
 
▪ Predefined screening questions of Prolific website will be used to target the sample (Appendix C)
 
▪ Participants who meet the inclusion/exclusion criteria will be emailed by Prolific and/or offered to complete our study on their Prolific account (Appendix D)
 
▪ Eligible participants who want to take part on the study will click on the start button and be redirected to our study website (Qualtrics)
 

INFORMED CONSENT	
 
▪ Participants will read the information sheet (Appendix E)
 
▪ Participants who want to proceed will tick a consent box (Appendix F)
 

RANDOMISATION	
 
▪ When starting the study, participants will be equally randomized to the four experimental conditions
 

BASELINE ASSESSMENTS	
 
▪ Participants will complete a baseline questionnaire on demographics (Appendix G)
 

MEAL CHOICE TASK	
 
▪ Instructions will be displayed (Appendix H)
 
▪ Dining-out scenarios will be displayed in randomised order
 
▪ For each dining out scenario, participants will be asked to choose their main meal and whether they would like to order a side and a dessert.
 

	Control condition	Energy labelling condition	Low energy increased availability condition	Low energy increased availability and energy labelling condition
HEALTH MOTIVATION	▪ Single-item Food Choice Questionnaire ( Appendix I )			
DEBRIEFING	▪ Aim guessing in an open-ended response format ▪ Insight on the participants' perception of the meal ordering task ( Appendix J ) ▪ Text to tell the participants what the study was about ( Appendix K )			
DATA MANAGEMENT	▪ The result files will contain: ○ Participant unique ID ○ Experimental condition participant is directed to ○ Food choices ○ Answers to questionnaires			

## 7. STATISTICAL ANALYSIS

All statistical analyses will be performed using SAS version 9.3 (SAS Institute, Inc., 2012 SAS® 9.3. Cary, NC). The level of significance will be set at  $p < 0.05$ . Linear mixed models will be fitted with PROC MIXED.

### 7.1. Participant's characteristics

A table will present the baseline characteristics by condition group and overall. The table will include gender, age, ethnic group, proportion of students, highest educational qualification, years in higher education, household income, subjective socioeconomic status, BMI, dieting status, dining-out frequency. Continuous variables will be summarised using means and standard deviations. Categorical variables will be summarised using counts and percentages.

### 7.2. Variables description

#### Primary outcome

The main outcome variable is the **energy of the main** selected in each dining out scenario in kcal.

#### Secondary outcome

##### **From the meal choice task:**

We will also calculate the **total energy** of the selected meal. It will be calculated by summing the kcal of the selected main, side and dessert.

##### **From the debriefing questionnaire:**

- **Validity of menu design** (item 2)
- **Validity of food offer** (items 4 and 5)
- **Kcal influence** (item 3)

Answers to all the items will be coded as: 1 = Strongly disagree; 2 = Disagree; 3 = Slightly disagree; 4 = Neither agree or disagree; 5 = Slightly agree; 6 = Agree; 7 = Strongly agree.

Internal dimension consistency of the items measuring *validity of food offer (for each cuisine)* will be assessed by calculating McDonald's  $\omega$  for each, which is an alternative to Cronbach's  $\alpha$  when the total test scores are normally distributed (i.e., all items are normally distributed) [32]. If adequate consistency is reached ( $\omega \geq 0.7$ ), *validity of food offer (for each cuisine)* score will be calculated as the mean of the two items constituting the dimension. In the case where internal consistency is not acceptable, we will run analyses separately on individual items.

### Independent variables

#### **SES**

##### **Level of education**

- **Highest educational qualification** will be coded from 1 = less than high school; 2 = high school completion; 3 = some college or associate degree; 4 = bachelor's degree; 5 = master's degree; 6 = doctoral or professional degree [33], [34] and as a binary variable as *lower* (values: 1 and 2) or *higher* (values: 3, 4, 5 and 6).
- **Years in higher education**, as a continuous variable.

Assuming that the two education variables are significantly correlated (tested using Pearson's  $r$ ) we will z-score the two variables and create an average of the two to form a composite score called '*level of education*'.

#### **Health motivation**

The health motivation score will be coded from 1 to 7 and correspond to the responses at the first and ninth items of the Single-item Food choice Questionnaire: "It is important to me that the food I eat on a typical day is healthy" and "It is important to me that the food I eat on a typical day helps me control my weight": 1 = Not at all important; 2 = Not important; 3 = Not very important; 4 = Neutral; 5 = Slightly important; 6 = Important; 7 = Very important.

#### **Cuisine familiarity**

- Familiarity condition: Binary variable based on the experimental design: 0 for unfamiliar cuisines and 1 for familiar cuisines
- Familiarity score: Ordinal variable based participants answer for each cuisine to the question "Have you ever tried [6 cuisines]?" coded as 1: Never tried; 2: Not in the last year; 3: Less than once per month; 4: 1-3 times per month; 5: 1-2 times per week; 6: 3 times per week or more

### Other variables

**Household income:** To be consistent with US census data [35], participants will report their annual household income before tax to the nearest \$1000.

**Subjective SES:** The measure of the Subjective Social Status using the MacArthur Scale will be coded from 1 to 10.

**BMI** will be calculated as weight (kg) / Height ( $m^2$ ). BMI data only will be trimmed for implausible values:  $BMI > 10$  or  $BMI < 60$  [36].

**Aim guessing:** Participants who identify the aim of the study as being to examine the influence of energy labelling or increased availability of lower energy food items on food choices will be coded as

being aware of the study aims. Responses will be independently coded by two researchers, with discrepancies in coding decisions resolved by a third researcher.

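### The BMI trimming rule has its inequalities reversed: as written it removes every BMI value, although only one descriptive row of the baseline table depends on it

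*Combined protocol and SAP*

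**What the plan says.** Section 7.2, Other variables, defines BMI as weight in kilograms divided by height in metres squared. It then says that "BMI data only will be trimmed for implausible values", and after the colon gives the two conditions, joined by an 'or': "BMI > 10$ or $BMI < 60$ [36" (the dollar signs and bracket are formatting and a citation number). The conditions therefore stand as the definition of what is implausible and to be trimmed.

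BMI appears in one other place in the analysis section. Section 7.1 lists it among the baseline characteristics to be tabulated by condition and overall: "subjective socioeconomic status, BMI, dieting status, dining-out frequency". Continuous variables in that table get means and standard deviations.

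The primary outcome in Section 7.2 is the energy of the main dish "selected in each dining out scenario in kcal"; BMI plays no part in it.

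In Appendix G, items 13 and 14 collect weight in a field marked kg and height in a field marked cm. Unlike the items on age, income, household size and the social ladder, they show no permitted entry range.

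**The concern.** A trimming rule has to separate values to keep from values to discard. This one cannot. Its two conditions overlap across the whole range from 10 to 60 and together cover every possible value. A programmer who codes the sentence as it stands sets every BMI to missing.

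At stake is the BMI row of the baseline table, which would be empty in all four conditions and overall. An analyst who notices must depart from the prespecified text without a documented reason. The rule is also the only plausibility check on BMI that the plan states.

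**Working it through.** **Inputs.** All come from Section 7.2, Other variables: the cut-offs 10 and 60, the two inequality signs, the connective 'or', and the stated purpose of removing implausible values. The source cited for the cut-offs was not available, so 10 and 60 are taken as given.

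**Step 1: logic.** A value escapes trimming only if it fails both conditions, that is, if BMI ≤ 10 and BMI ≥ 60. No number does both, so nothing escapes.

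**Step 2: check on a grid.** BMI values from 0.1 to 150.0 in steps of 0.1 give 1,500 values. Four readings were compared:

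| Reading | Trimmed | Kept |
|---|---|---|
| As written: trim if BMI > 10 or BMI < 60 | 1,500 | 0 |
| Same conditions read as what to keep | 0 | 1,500 |
| 'Or' read as 'and': trim if BMI > 10 and BMI < 60 | 499 | 1,500 − 499 = 1,001 |
| Signs reversed: trim if BMI < 10 or BMI > 60 | 999 | 501 (10.0 to 60.0) |

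The first reading discards everything and the second discards nothing. The third discards the plausible values and keeps the rest. Reversing the signs does what the sentence says it is for: 18.5, 25, 30 and 40 are kept, while 5, 9.9, 60.1 and 80 are trimmed.

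**Step 3: where BMI is used.** The rest of the analysis section was read for any dependence on BMI.

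- Primary and secondary outcomes (7.2): energy of the main, total meal energy and debriefing items. No BMI.
- Main and stratified models (7.4): labelling, availability, educational qualification and familiarity. No BMI.
- Sensitivity analyses (7.4): exclusion of those who guessed the aim, and a different education variable. No BMI.
- Moderated mediation and debriefing analyses (7.5): no BMI.
- Sample size (7.6): no BMI.
- Missing data (7.3): exclusions are for not finishing the study, failed attention checks and ineligibility. An implausible BMI is not among them.

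The reach of the error is the single baseline row.

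**The case against.** The strongest reply is that this is a slip of the pen that no one would act on. The same sentence gives the purpose, no analyst would call every BMI implausible, and an empty row would expose the mistake at once. The two sensible repairs also agree: discarding values below 10 or above 60, and keeping values between 10 and 60, differ only at exactly 10 and exactly 60. All of this stands, and it limits the severity. It does not make the written rule correct.

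A reader might infer more than the documents support, in three ways.

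- **That comparability of the arms is at risk.** Section 7.1 plans means and standard deviations, with no test between arms on BMI, and no model adjusts for it. An empty row would be a gap in description; it would not bias any estimate.
- **That participants would be lost.** The rule is confined to BMI data, so a trimmed BMI leaves the participant in every analysis.
- **That entry in kg and cm by US residents is part of the same error.** The arithmetic of a possible mix-up is sound. At 170 cm, 150 lb typed as 150 kg gives 150/1.70² = 51.9 and survives even the corrected rule, against a true value of 150 × 0.4536/1.70² = 23.5; 180 lb typed as kg gives 180/1.70² = 62.3 and is trimmed. But this assumes pounds in the weight field together with a correct height in centimetres. Someone using customary units in both fields, for example 150 and 67, would produce 150/0.67² = 334 and be trimmed. The fields are labelled kg and cm, and the documents give no rate for any of these errors. This is a suggestion about questionnaire design and does not show the trimming rule to be wrong.

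**Conclusion.** The rule is wrong as written. It removes 100% of BMI values, and no literal reading of its 'or' separates plausible from implausible ones. The conclusion rests on the printed signs, both of which are legible, and on the absence of any correcting statement elsewhere. That the intended limits are 10 and 60 with the signs reversed is an inference from the stated purpose, though a very safe one.

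The size is small: one descriptive row. No estimate, test, power figure or participant's inclusion changes. It should be treated as a low-severity correction to the SAP.

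**What to change.** In Section 7.2, Other variables, replace the rule with: BMI < 10 or BMI > 60 will be set to missing. The sponsor should confirm the two cut-offs against the cited source when making the change. A short clause saying that the participant stays in all other analyses would spell out what the present wording already implies. Reporting the number of trimmed values beneath the baseline table would also be sensible.

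The cost is two symbols and a few words, and no other analysis is touched. Offering pounds and feet/inches as an alternative entry format in Appendix G, with conversion to kg and m, is optional and can be decided separately.

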### 7.3. Missing data

We do not anticipate missing data on the primary outcome and dependant variables because the online study will not allow missing answers. Data from participants who start but not finish the study will not be analysed. Submissions of participants who fail the attention checks or do not pass eligibility criteria will not be analysed. Any *a posteriori* withdrawal will be reported and reasons for withdrawal will be documented (e.g., incorrect answers, technical problems).

### 7.4. Main analyses

The measure of SES used in our primary analysis will be the *highest educational qualification* (categorical variable: *lower vs. higher*) because previous research showed that people with college education were more likely to use kcal labels at restaurants [37]. The measure of health motivation will be the response to the first item from the Single-item Food choice Questionnaire: “It is important to me that the food I eat on a typical day is healthy”, i.e., importance of healthiness.

First, we will examine whether our manipulation of familiarity is valid by examining the proportion of participants that are familiar / unfamiliar with each cuisine menu type (i.e. we expect >75% of participants to be familiar with our chosen ‘familiar’ cuisines and <25% of participants to be familiar with our ‘unfamiliar’ cuisines). We will also report the mean and SD of the *familiarity score* for each cuisine.

A linear mixed model will be used to test the effect of *labelling* (categorical, between-subject), *availability* (categorical, between-subject), *highest educational qualification* (categorical, between-subject), *familiarity* (categorical, within-subject) and *labelling\*highest educational qualification*, *availability\*highest educational qualification*, *labelling\*familiarity*, *availability\*familiarity*, interactions on *energy of the main* for the six dining out scenario. A random effect of participant will be added by using an unstructured covariance structure to account for correlation between repeated ordering by the same participant.

If any interactions with *familiarity* are significant, analysis will be stratified by *familiarity* and two linear mixed models will be fitted to examine the effect of *labelling*, *availability*, *highest educational qualification* and *labelling\*highest educational qualification*, *availability\* highest educational qualification* interactions on *energy of the main* for familiar and unfamiliar cuisines with participant effect as random to account for correlation between repeated ordering by the same participant for familiar and unfamiliar cuisines.

If the above analyses reveals a significant interaction between *labelling* or *availability* condition and *highest educational qualification* on *energy of the main*, analysis will be stratified by *highest educational qualification (lower vs. higher)* and two linear mixed models will be fitted to examine the effect of *labelling* and *availability* on *energy of the main* for lower and higher educational qualifications.

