### 4. PARTICIPANTS AND RECRUITMENT

#### 4.1. Recruitment

Participants will be recruited through an online recruitment panel (Prolific) in which participants are compensated proportionate to the time it takes to complete the online study ( $\approx \$6$ /hour reward participants). Participants' recruitment will be stratified by gender (50% male, 50% female), student status (8% yes and 92% no) [24] and highest achieved education level (10% less than high school, 30% high school completion, 30% some college or associate's degree, 20% bachelor's degree, 10% advanced degree) to be representative of US adults [25].

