### 2. *Age*

- \_\_ (free text; range of 25-99)

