**15. How hungry do you feel?**

---

0 100  
Not at all hungry As hungry as I've ever felt

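### Gender, age and baseline hunger are collected before the menus but enter no planned model, which leaves a modest and nearly costless gain in precision unused

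*Combined protocol and SAP*

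**What the plan says.** Section 7.4 lists the fixed effects of the primary model in full. The sentence opens "A linear mixed model will be used to test the effect of" and names labelling, availability, education (lower or higher), familiarity, and the interactions of each intervention with education and with familiarity. It then adds: "A random effect of participant will be added by using an unstructured covariance structure". The follow-up models stratified by familiarity or education bring in no further variables. The sensitivity analyses remove aim guessers or swap the education measure. The secondary analyses add health motivation and the debriefing items.

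The study flow in Section 6 has this step after randomisation and before the meal choice task: "Participants will complete a baseline questionnaire on demographics". That questionnaire (Appendix G) asks gender (Male, Female, Other), age ("free text; range of 25-99") and, as item 15 on a 0 to 100 scale, "How hungry do you feel".

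Gender and age are used in the baseline description (Section 7.1: "The table will include gender, age, ethnic group, proportion of students"), and gender also as a recruitment quota (Section 4.1: "recruitment will be stratified by gender (50% male, 50% female"). Hunger is not in the baseline table or anywhere else in the analysis plan.

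**The concern.** Labelling, availability and their interactions with education compare different people. Their precision is limited mainly by how much participants differ from one another, and asking each person to choose from six menus does not reduce that component. Participant-level covariates measured before the menus can reduce it.

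All three variables are valid for this purpose. They are recorded before the participant meets the assigned menus, so condition cannot have shaped the answers. They should also be complete, because Section 7.3 says the platform does not accept missing answers. Leaving them out forgoes whatever precision they offer on the primary objective. Collecting hunger without a declared use also leaves the choice of adjustment open until the data have been seen.

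**Working it through.** **Inputs.** From Section 7.6: level 1 and level 2 variance 47,244 each, 6 choices per participant, 1,000 participants analysed. (That section also gives 47,224 for the earlier trial; the difference is immaterial here.) From Section 6: equal allocation to four conditions, so 500 against 500 for each factor. From Section 4.1: "10% less than high school, 30% high school completion", so 40% lower and 60% higher education. Two-sided alpha of 0.05 is assumed, since sidedness is not stated.

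**The plan's own figure.** Section 7.6 states power 0.93 for a 2% reduction, without naming the base for the 2%.

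- Variance of a participant mean = 47,244 + 47,244/6 = 55,118. Six-sevenths of this is between-participant variance.
- SE of a factor effect = sqrt(55,118 × 4/1,000) = 14.85 kcal.
- With 2% of 706 kcal (the no-label mean in Section 7.6) = 14.1 kcal, power is 0.156.
- With 2% of 973 kcal (the mean of the ten American mains in Appendix A) = 19.5 kcal, power is 0.258.

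The stated 0.93 does not reproduce on either base. That is a separate problem. Only the SE is carried forward.

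**Effect of adjustment.** Let R² be the share of between-participant variance explained by gender, age and hunger beyond what is already in the model. The documents give no value, so a range is assumed. Participant-level covariates leave the level 1 variance unchanged:

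SE = sqrt(((1 − R²) × 47,244 + 47,244/6) × 4/1,000)

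The equivalent gain in sample size is the ratio of 55,118 to the reduced variance, minus 1.

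| Assumed R² | Variance of participant mean | SE (kcal) | Equivalent extra participants | Power for 47 kcal |
|---|---|---|---|---|
| 0 | 55,118 | 14.85 | 0% | 0.886 |
| 0.02 | 54,173 | 14.72 | 1.7% | 0.891 |
| 0.05 | 52,756 | 14.53 | 4.5% | 0.899 |
| 0.10 | 50,394 | 14.20 | 9.4% | 0.912 |
| 0.20 | 45,669 | 13.52 | 20.7% | 0.935 |

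The 47 kcal is the literature effect of labelling quoted in Section 7.6.

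**Interactions with education.** SE = sqrt(variance × (4/400 + 4/600)). This is 30.3 kcal unadjusted, 29.0 at R² = 0.10 and 27.6 at R² = 0.20.

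**Interactions with familiarity.** Each participant contributes the mean of three familiar choices minus the mean of three unfamiliar ones, so the participant effect cancels. The variance is 2 × 47,244/3 = 31,496, and SE = sqrt(31,496 × 4/1,000) = 11.22 kcal with or without the covariates.

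**If the covariates predict nothing.** Gender in three categories, age and hunger cost 2 + 1 + 1 = 4 degrees of freedom among 1,000 participants. A simulation at R² = 0 gave an SE of 14.87 kcal unadjusted and 14.89 adjusted.

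**Sensitivity to the variance split.** If only 20% of the same total variance lay between participants, the SE would be 11.22 kcal unadjusted, 10.88 at R² = 0.10 and 10.53 at R² = 0.20. The gains would be worth 6.4% and 13.6% more participants.

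**The case against.** The strongest reply is that nothing here is wrong. Conditions are randomised, so the unadjusted contrasts are valid, and a sparse model is a defensible choice. That stands, and it is why the point concerns efficiency only.

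The second reply is that nobody has shown these variables to be prognostic. This also stands. The only predictor correlation with energy ordered in the documents is for healthiness motivation in an earlier trial (r = −0.25, so 0.25² is about 6% of variance). That is a different variable, and in this study it is measured after the task. It says nothing direct about gender, age or hunger, and nothing in the documents supports the upper end of the range.

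Third, the change is not quite a single sentence. Gender has an Other category. The age field starts at 25 although Section 4.2 admits adults from 18. Education is not randomised, so its main effect changes meaning once age and gender are in the model. These points call for careful wording but do not defeat the change.

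Three stronger readings are tempting, and the documents do not support them:

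- A reader might infer that the omission biases the intervention effects. It does not.
- A reader might take the gender quota as a randomisation stratum that must therefore be in the model. Section 4.1 describes quotas for recruitment, and Section 6 describes only equal allocation.
- A reader might note that the SE of 14.85 kcal exceeds 2% of 706 kcal and expect adjustment to rescue the power. The plan names no base for the 2%, and on 973 kcal the comparison reverses. Even at R² = 0.20, power for 14.1 kcal rises only from 0.156 to 0.180.

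**Conclusion.** The point holds as a low-cost improvement. Three valid covariates measured before the menus are available and unused, and one of them has no declared purpose. Across an assumed R² of 0.02 to 0.20, the SE of the between-participant effects falls by about 1% to 9%. The benefit reaches labelling, availability and their education interactions, which carry the primary objective. It does not reach the labelling by familiarity and availability by familiarity contrasts, so the secondary objective on familiar and unfamiliar cuisines is unaffected.

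The sizes rest on the plan's variances and on an R² that the documents do not give. The true gain could be close to zero. The case for acting is that the possible loss is negligible.

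**What to change.** In Section 7.4, before data are seen:

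- Prespecify gender, age (continuous) and baseline hunger (0 to 100) as fixed covariates in the main model and in every stratified model.
- State the coding rule for gender Other.
- Use the same covariates in the moderated mediation of Section 7.5, so that the analysis triggered by the main model's interactions is adjusted in the same way.
- Add the unadjusted model to the sensitivity analyses.
- Note that the education main effect is then conditional on the added covariates, including age and gender.
- Reconcile the 25 to 99 age field in Appendix G with inclusion from age 18 in Section 4.2, so that age can be entered correctly for everyone eligible.

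The cost is a short SAP paragraph, a check of the age field and about four degrees of freedom. No new data are needed.
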